2.2. Background

2.2.1. LAM-002A Mechanism of Action

Viral entry into cells has been shown to occur through components of the endosomal network, including Rab9 GTPase, the endo/lysosomal cholesterol transporter Niemann-Pick C1 (NPC1) (Murray et.al; 2005; Carette et. al., 2011), and phosphatidylinositol-3-phosphate 5-kinase (PIKfyve) (Murray et.al; 2005; Carette et. al., 2011; Nelson et.al., 2017; Qiu et.al., 2018). PIKfyve, is a 240-kDa endosomal phosphatidylinositol (PI) 5 lipid kinase that catalyzes the phosphorylation of phosphatidylinositol 3-phosphate (PI(3)P) to phosphatidylinositol 3,5-bisphosphate (PI(3,5)P₂). PIKfyve regulates endosome and lysosome biogenesis and intracellular trafficking, facilitating late-endosome-to-trans-Golgi vesicular transport. This vesicular transport is part of the endosomal network that viruses use to enter the cell and replicate, suggesting PIKfyve inhibition can inhibit viral entry into cells and decrease viral replication.

LAM-002A is a first-in-class inhibitor of PIK fyve with an IC₅₀ of 14nM, and K_d of approximately 75 pM (range 69-81 pM). The potential of LAM-002A to inhibit coronavirus viral entry has been tested *in vitro*. Apilimod potently blocked the entry of severe acute respiratory syndrome (SARS) and Middle East respiratory syndrome (MERS) pseudotyped virus at all concentrations tested (62.5-250 nM) which has been independently replicated by Ou et.al., 2020. Importantly apilimod also blocked the entry of lentiviral pseudovirions expressing the SARS-CoV-2 S glycoprotein and displayed activity against several independent clinical isolates of SARS-CoV-2 (Ou et. al., 2020; Riva et al, 2020; Kang et al, 2020). Furthermore, combinatorial activity was observed with remdesivir suggesting that greater antiviral efficacy may be achieved with apilimod in combination with other anti-viral agents. Taken together, the effect on endolysosomal trafficking and in vitro anti-viral activity indicate that LAM-002A, the dimesylate salt of apilimod, has promising therapeutic potential for treating SARS-CoV-2 infections.

LAM-002A has also been found to potently inhibit the production of T-helper lymphocyte type 1 (Th1) cytokines IL-12 and IL-23 in PBMCs when treated with multiple toll-like receptor (TLR) stimuli (LAM-002A IB V4). In addition, LAM-002A inhibits IL-6 in response to IFN- γ /SAC (Wada et.al, 2007). Significant reduction of IL-12 and IL-23 transcripts, with a simultaneous increase in IL-10 was also observed in the skin lesions of psoriatic subjects treated with apilimod at 70 mg of apilimod free base QD (Wada et.al, 2012). While the stimuli and role of specific cytokines in COVID-19 are not known, these data suggest that LAM-002A has the potential to repress pro-inflammatory cytokines (e.g. IL-12, IL-23) and induce anti-inflammatory cytokines (e.g. IL-10).

2.2.2. Human Experience with LAM-002A

In addition to its anti-viral mechanism of action, the study rationale for LAM-002A in subjects infected with SARS-CoV-2 is based on the well-established safety and tolerability profile of the molecule in human trials.

2.2.2.1. Safety and Tolerability

LAM-002A has a well-established clinical record supporting its safety and tolerability, including published literature (LAM-002A IB V5). Under IND 125,763, AI Therapeutics sponsored a

Phase 1 dose-ranging and expansion study evaluating the safety, pharmacokinetics, pharmacodynamics, and anticancer activity of LAM-002A in subjects with recurrent, previously treated non-Hodgkin lymphoma (NHL). Study results indicate that LAM-002A is very well tolerated and has a favorable safety profile at doses of ≤ 125 mg BID (250 mg total daily dose). To date, >700 study subjects have received apilimod dimesylate or apilimod, including 186 healthy subjects participating in clinical pharmacology studies, 468 subjects with nonmalignant inflammatory conditions (psoriasis, rheumatoid arthritis, Crohn's disease), and 62 subjects with B-cell hematological cancers.

Most observed adverse events or laboratory abnormalities have been low-grade, infrequent, and largely attributable to the underlying disease, prior therapy, concomitant medications, or other conditions. Continuous oral administration of LAM-002A has been well tolerated in humans with dosing regimens of \leq 125 mg BID (\leq 250 mg total daily dose). In subjects with cancer, dosing regimens of 150 mg BID (300 mg QD) or 75 mg TID (225 mg QD) were not well tolerated due to symptoms of nausea, vomiting, and diarrhea that effectively precluded drug compliance in most subjects.

2.2.2.2. LAM-002A Pharmacokinetics in Humans

The pharmacokinetics of LAM-002A was studied in healthy subjects and in subjects with hematological cancers as a monotherapy and in combination with rituximab, or atezolizumab. LAM-002A (apilimod free base of LAM-002A) was rapidly bioavailable following oral dosing with an approximate T_{max} of 1 hour. The C_{max} and AUC₀₋₈ generally increased with increasing dose; the Day 8 AUC₀₋₈ showed the closest relationship to dose proportionality. As steady-state exposures were achieved, mean Day 8/Day 1 accumulation indices (AI) for C_{max} and AUC₀₋₈ across all dose levels were 1.3 and 1.7, respectively. Mean terminal $t_{1/2}$ values ranged from 2.7 to 3.9 hours on Day 1 and from 5.4 to 7.0 hours on Day 8 and did not show dose dependency. On the first day of administration, ~90% of the drug was cleared within 10 hours after which the remaining drug was eliminated with a terminal $t_{1/2}$ of 5 to 10 hours. The terminal $t_{1/2}$ increased to 12 to 21 hours on Day 14 in healthy subjects.

2.3. Benefit/Risk Assessment

More detailed information about the known and expected benefits and risks and reasonably expected adverse events of LAM-002A may be found in the LAM-002A IB V5.

There have been no subjects with COVID-19 or SARS-CoV-2 exposures evaluated to date, and the risk/benefit of LAM-002A in COVID-19 is not understood. The safety and tolerability of LAM-002A has been established, with >800 subjects treated with the drug as of March 20, 2020. Overall, product administrations were well tolerated. Gastrointestinal TEAEs of nausea, vomiting, and diarrhea were commonly observed, and showed dose dependency, with most TEAEs being of Grade 1 or 2. At 125 mg BID, LAM-002A was found to be safe and tolerable.

No vaccine prophylaxis exists for SARS-CoV-2 infection and only one antiviral agent, remdesivir, has been approved under an emergency-use authorization for therapy for COVID-19. Remdesivir has modest activity and must be given intravenously (IV), thus limiting its utility for outpatient care of subjects with mild COVID-19 symptoms. While anti-viral efficacy of LAM-002A has not been established in humans or in animal models, the in vitro anti-viral activity suggests it may have potential efficacy in humans. Development of a well-tolerated, easy-to-administer oral therapy for treatment of subjects with COVID-19 could prevent disease progression and consequent morbidity, the need for intensive care, and mortality.

A planned interim analysis with DSMB review early in the trial after 15 subjects in each treatment arm have completed treatment ensures the mitigation of any unanticipated safety risk in this COVID-19 population.

3. STUDY OBJECTIVES

3.1. Primary Objective

• To evaluate the antiviral efficacy of LAM-002A in subjects with COVID-19 with a baseline viral load >10⁵ copies/mL as measured by SARS-CoV-2 clearance as determined by a qRT-PCR test from nasopharyngeal samples at Day 4 (72 hours ± 4 hours post the first drug dose)

3.2. Secondary Objectives

- To evaluate the safety and tolerability of LAM-002A administration in the treatment of subjects with mild COVID-19.
- To evaluate the efficacy of LAM-002A in preventing COVID-19 disease progression in subjects who have proven infection with the SARS-CoV-2 virus as determined by a validated test; disease progression is defined as the occurrence of any of the following:
 - Death at Day 28
 - Hospitalization at Day 28
- To evaluate change in COVID-19 clinical status, as defined by the ordinal scale, of subjects treated with LAM-002A compared to placebo at Day 28, in subjects who become hospitalized and continue LAM-002A/placebo treatment.
- To compare the proportion of subjects at or above 95% oxygen saturation (O₂ sat) between LAM-002A versus placebo treatment groups as measured on Days 1, 4, and 11.

3.2.1. Safety and Tolerability

• To evaluate the safety and tolerability of LAM-002A administration in the treatment of subjects with COVID-19.

3.2.2. Clinical Efficacy

- To evaluate the efficacy of LAM-002A in preventing COVID-19 progression in subjects who have proven infection with the SARS-CoV-2 virus as determined by a validated test; disease progression is defined as the occurrence of any of the following:
 - Death at Day 28
 - Hospitalization at Day 28

3.2.3. Clinical Status

• To evaluate change in COVID-19 clinical status as defined by the ordinal scale of subjects treated with LAM-002A compared to placebo at Day 28, including the subjects who become hospitalized and continue LAM-002A/placebo treatment.

3.2.4. Oxygen Saturation

• To compare the proportion of subjects at or above 95% oxygen saturation (O2 sat) between LAM-002A versus placebo treatment groups as measured on Days 1, 4 and 11.

3.3. Exploratory Objectives

3.3.1. Pharmacokinetic

• To potentially evaluate the pharmacokinetics of LAM-002A in subjects with mild COVID-19.

3.3.2. Viral Clearance

- To potentially evaluate the antiviral efficacy of LAM-002A in subjects with COVID-19 with a baseline viral load >10⁵ copies/mL as measured by SARS-CoV-2 clearance as determined by a qRT-PCR test from saliva samples at Day 4.
- To potentially evaluate the antiviral efficacy of LAM-002A in subjects with COVID-19 with a baseline viral load >10⁵ copies/mL as measured by SARS-CoV-2 clearance as determined by a qRT-PCR test from saliva samples at Day 11.
- To potentially evaluate the antiviral efficacy of LAM-002A in subjects with COVID-19 with a baseline viral load >10⁵ copies/mL as measured by SARS-CoV-2 clearance as determined by a qRT-PCR test from saliva samples at Day 28.
- To potentially evaluate the antiviral efficacy of LAM-002A in subjects with COVID-19 with a baseline viral load >10⁵ copies/mL as measured by SARS-CoV-2 clearance as determined by a qRT-PCR from saliva samples at all available days based on AUC analysis.
- To potentially evaluate the difference in proportion of subjects with a SARS-CoV-2 viral load <LLOQ between the LAM-002A and the placebo arm as measured by a qRT-PCR test from nasopharyngeal samples at Day 4.

3.3.3. Pharmacodynamic Objectives

- To potentially evaluate the effect of LAM-002A on target engagement biomarkers.
- To potentially evaluate the effect of LAM-002A on pro- and anti-inflammatory cytokine levels in plasma of COVID-19 subjects.

3.3.4. Genetic Evaluation Objectives

- To potentially evaluate viral resistance by comparing genomic sequence of SARS-CoV-2 before and after LAM-002A treatment.
- To potentially evaluate the effect of SARS-CoV-2 genetic variants on LAM-002A efficacy.
- To potentially evaluate the effect of germline DNA sequence polymorphisms on LAM-002A safety and efficacy.

4. STUDY ENDPOINTS

4.1. Primary Endpoint

• The primary efficacy outcome measure evaluates change in SARS-CoV-2 viral load at Day 4 from Day 1, of LAM-002A or placebo-treated subjects. SARS-CoV-2 viral load will be measured by a qRT-PCR test of nasopharyngeal samples. Analysis will focus on log₁₀ viral load on Day 4 compared to baseline viral load at Day 1 in subjects with baseline viral load >10⁵ copies/mL.

4.2. Secondary Endpoints

4.2.1. Safety and Tolerability

• The proportion of LAM-002A-treated subjects who develop TEAEs compared to placebo.

4.2.2. Clinical Efficacy

- The proportion of subjects treated with LAM-002A compared to placebo, who have disease progression by Day 28 as defined by the occurrence of:
 - \circ Hospitalization
 - o Death

4.2.3. Clinical Status

- Change in COVID-19 clinical status as defined by the ordinal scale, of subjects treated with LAM-002A compared to placebo at Day 28, in subjects who become hospitalized and continue LAM-002A/placebo treatment, based on the following scores:
 - 1. Not in the hospital
 - 2. Hospitalized, requiring low flow supplemental oxygen (such as nasal cannula)
 - 3. Hospitalized, not on invasive ventilation (such as 100% non-rebreather, BIPAP), (pre-ICU)
 - 4. Hospitalized, in the ICU, on invasive ventilation or ECMO
 - 5. Dead

4.2.4. Oxygen Saturation

• Proportion of subjects at or above 95% oxygen saturation (O2 sat) between LAM-002A versus placebo as measured on Days 1, 4, and 11.

4.3. Exploratory Endpoints

4.3.1. Pharmacokinetics

- Plasma concentration time profile of LAM-002A, on Day 1 pre-dose, at 1 (± 15 min) and 2 (± 15 min.) hr, and at trough on Day 11 will potentially be determined in a subset of subjects (target 20 subjects) to evaluate the deviation of pharmacokinetic parameters from expected exposure, and correlation of pharmacokinetic parameters with safety and efficacy.
- Maximum observed concentrations within the bounds of the sampling time points and trough concentration on Day 11.

4.3.2. Viral Clearance

- Change from baseline (Day 1, Pre-dose) of SARS-CoV-2 viral load as measured by a qRT-PCR test from saliva samples on Day 4, compared between the LAM-002A arm and the placebo arm in subjects with a baseline viral load >10⁵ copies/mL.
- Change from baseline (Day 1, Pre-dose) of SARS-CoV-2 viral load as measured by a qRT-PCR test from saliva samples on Day 11, compared between the LAM-002A arm and the placebo arm in subjects with a baseline viral load >10⁵ copies/mL.
- Change from baseline (Day 1, Pre-dose) of SARS-CoV-2 viral load as measured by a qRT-PCR test from saliva samples on Day 28, compared between the LAM-002A arm and the placebo arm in subjects with a baseline viral load >10⁵ copies/mL.
- Difference in SARS-CoV-2 viral load as measured by a qRT-PCR test from saliva samples based on AUC(_{Day1-Day11}), between the LAM-002A arm and the placebo arm in subjects with a baseline viral load >10⁵ copies/mL.
- Difference in SARS-CoV-2 viral load as measured by a qRT-PCR test from saliva samples based on AUC(_{Day1-Day28}), between the LAM-002A arm and the placebo arm in subjects with a baseline viral load >10⁵ copies/mL.
- Difference in proportion of subjects with a SARS-CoV-2 viral load <LLOQ as measured by a qRT-PCR test from nasopharyngeal samples between the LAM-002A and the placebo arm at Day 4.

4.3.3. Pharmacodynamics

• Changes in the expression of target engagement biomarkers in the nasal epithelium, PBMCs, and plasma.

4.3.4. Immunogenicity Endpoints

• Changes in plasma levels of IL-12, IL-23, and IL-6, IFN-γ, IL-10 and GM-CSF (additional cytokines may be analyzed in parallel).

4.3.5. Genetic Endpoints

• Changes in viral genome sequence before and after LAM-002A treatment.

- Effect of SARS-CoV-2 genetic variants on efficacy (% of subjects that progress per variant), as determined by viral genome sequencing.
- Effect of genetic polymorphisms on LAM-002A safety and efficacy.

5. STUDY DESIGN AND CONDUCT

5.1. Study Design

This is a double-blind, randomized, placebo-controlled Phase II study for the treatment of SARS-CoV-2 positive outpatient individuals with LAM-002A. The study will compare the active arm of LAM-002A plus standard of care, with the control placebo arm plus standard of care. This study will be conducted in approximately 142 adult subjects ages ≥ 18 , with ≤ 8 days of symptom onset, who are SARS-CoV-2 positive as determined by a validated test. The study will enroll subjects who have at least one of the following COVID-19-related symptoms indicating mild disease: fever (temperature ≥ 100.4), anosmia (loss of taste or smell), cough, sore throat, gastrointestinal complaints (e.g. nausea, vomiting or diarrhea), chills, congestion or runny nose, headaches, muscle or body aches, fatigue, without shortness of breath or dyspnea (RR<20, SpO2 >93% on room air), or asymptomatic patients who have tested positive for COVID-19 via a validated test within the past 4 days. Subjects will be treated with 125 mg LAM-002A PO, BID, or with placebo PO, BID for 10 days (20 doses). The treatment schedule is outlined in the Schedule of Activities (SoA), Table 1. Subjects will be followed at 4, 6, 8, 11, 22 and 28 days after the treatment start.

Subjects will be randomized using a permuted block scheme (with variable block size) in a 1:1 ratio to one of the two groups: (1) LAM-002A, or (2) placebo. To assure at least 71 placebo participants have a viral load $\ge 2 \times 10^3$ copies/mL (the lower limit of detection of the assay) at Day 4, 142 participants with baseline viral load $\ge 10^5$ copies/mL will be enrolled to achieve the primary objective; thus, an expected 142 subjects will be randomized (71 to receive LAM-002A and 71 to receive placebo). Because the existing longitudinal data on viral load in subjects are preliminary, this baseline viral load and number of participants randomized may be adjusted to allow for 71 placebo participants above the lower limit of detection of the assay ($\ge 2 \times 10^3$ copies/mL) at Day 4 so that a difference in viral clearance between the groups can be assessed.

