The study will incorporate an interim safety analysis after the first 30 subjects (15 on LAM-002A and 15 on placebo) have completed treatment and have been followed up for 11 days post-first dose. Recruitment and randomization will continue while this analysis is conducted. An additional interim analysis will be conducted at 50% of total enrollment. Recruitment and randomization will continue while this analysis is conducted. Recommendations from an independent DSMB will be used for decision of early termination or design adaptations.

Primary analysis of antiviral efficacy will be conducted in the subgroup of randomized participants with a baseline viral load > 10^5 copies/mL. As existing data on viral load is preliminary, this baseline may be adjusted as detailed in the statistics section. Non-parametric and parametric statistical analysis will be conducted as appropriate. For the comparison of the LAM-002A active arm and the control arm for the primary endpoint and secondary endpoints of drug effect, appropriate methods will be employed. Baseline subject characteristics, study therapy administration/compliance, safety, supportive care administration, and pharmacokinetics will be analyzed descriptively.

Product Description:

LAM-002A (apilimod dimesylate) is a first-in-class inhibitor of phosphatidylinositol-3-phosphate 5-kinase (PIKfyve) that has demonstrated *in vitro* anti-viral activity against SARS-COV-2 infected cells.

Each Size 0 capsule of the active drug contains 25 mg of LAM-002A (equivalent to 17.1 mg of apilimod free base). Inactive components in the capsules are microcrystalline cellulose, silicified microcrystalline cellulose, anhydrous lactose, croscarmellose sodium, colloidal silicon dioxide, and magnesium stearate.

Each Size 0 capsule of the placebo is identical in appearance to capsules containing the active drug. Each placebo capsules contains microcrystalline cellulose as the inactive ingredient.

All inactive excipients are within the limits of FDA's Inactive Ingredient (IIG) limit requirements.

Study Activities:

The specific study procedures and timing of activities to be conducted for each subject enrolled in the study are presented in tabular form in Table 1. Physical examinations, other clinical evaluations, and additional laboratory studies or more frequent assessments may be performed consistent with appropriate medical care for the subject, but these data will not necessarily be collected unless specified in Table 1.

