5.2. Study Conduct

The study will be performed in accordance with the principles as set forth under the requirements of 21 Code of Federal Regulations (CFR) 50 and the ICH E6 GCP guideline. The research will be overseen by an institutional review board/independent ethics committee (IRB/IEC). The study protocol, any protocol amendments, informed consent documents, and any material used to describe the trial to potential subjects will be reviewed and approved by the IRB/IEC prior to the performance of any study-related procedures.

AI Therapeutics, Inc. will serve as the regulatory sponsor for the study and will maintain an investigational new drug (IND) application with the FDA. The protocol will be submitted to an IND for LAM-002A (IND#148521) and the trial design and results will be subject to review by the FDA.

A designated clinical research organization (CRO) will serve as the operational coordinator of the study and will oversee conduct of the study at participating study centers. The CRO will perform activities relating to pharmacovigilance; site monitoring; data management and study reporting; and sample handling.

The study will employ an independent Data Safety Monitoring Board (DSMB) for safety and clinical efficacy and analysis of viral clearance efficacy data. AEs and serious adverse events (SAEs) will be reviewed by the DSMB on an ongoing basis to identify any safety concerns. Conference calls among the members of the DSMB will be conducted periodically to discuss study progress, exchange study information, and review safety events (in particular, DLTs; SAEs; adverse events of special interest; and AEs leading to dose interruption, dose reduction, or therapy discontinuation), and discuss potential amendments to the protocol.

The DSMB will be responsible for reviewing the interim safety and efficacy analyses and recommending study continuation, termination, or adaptation. An interim safety analysis of study data will be performed after the first 30 subjects (15 on LAM-002A and 15 on placebo) have completed treatment and have been followed up for 11 days post-first dose. During the analysis, study enrollment will not be halted. Recommendations from the DSMB will be used for decision of early termination, continuation, or study design adaptations.

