5.3. Rationale for Study Design

The study is a randomized, placebo controlled, multi-center study in approximately 142 adults ages \geq 18, randomized to LAM-002A or placebo in a 1:1 ratio. The study has been designed to provide data on the efficacy, safety, pharmacokinetics, and pharmacodynamics of LAM-002A in subjects with mild COVID-19 symptoms. After exposure with SARS-CoV-2, there is approximately a 5-day incubation period (range 1-14 days) (Guan et. Al., 2020; Li et.al., 2020; Lauer et. Al., 2020), after which most individuals (~80%) develop a mild disease. The study has been designed to treat individuals with antiviral LAM-002A early in the infection period, to reduce the viral load of SARS-CoV-2 and prevent COVID-19 progression.

In order to mitigate unanticipated safety issues in this COVID-19 population, an early interim safety analysis after 30 subjects (15 on LAM-002A and 15 on placebo) have been treated and followed for 11 days, will be performed, and reviewed by a DSMB for decision on study continuation, termination or study adaptation.

The primary outcome measure is reduction in SARS-CoV-2 viral load measured in nasopharyngeal samples at Day 4 in LAM-002A treated subjects compared to those on placebo. Exploratory outcome measures of SARS-CoV-2 viral load from saliva samples at Days 1, 4, 11, and 28 are included to further inform on the rate of viral clearance. For the primary and secondary objectives examining antiviral efficacy, the analysis will focus on the subgroup of randomized subjects with baseline viral load > 10⁵ copies/mL. This subgroup was chosen because subjects in this group are predicted to have sufficient viral load at baseline for the study drug to show benefit when compared to placebo. Because the existing longitudinal data on viral load in participants are preliminary, this baseline viral load and number of participants randomized may be adjusted to allow for 71 placebo participants above the lower limit of detection of the assay (\geq 2228 copies/mL; see Section 10.1) at Day 4 such that a difference in viral clearance between the groups can be adequately assessed. Nasopharyngeal swabs to evaluate baseline viral load will be performed prior to randomization; however, results on viral load will not be available prior to initiation of treatment. Supportive analyses for viral load outcomes will be performed in all randomized participants.

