12.2. Sample Size Determination

The study is designed to have high power at a moderate significance level to detect a signal of benefit for the viral load outcome. The sample size calculation is based on the primary endpoint of interest: log₁₀ respiratory (nasopharyngeal swab) viral load at Day 4 post-randomization.

Given the limited data on the variability of the change in log_{10} viral load, the study is powered based on detecting a moderate standardized effect size of 0.3 using an analysis of covariance (ANCOVA), adjusting for baseline log_{10} viral load. (NOTE: For ANCOVA, the effect size is the standard deviation of the treatment means divided by the pooled standard deviations of the observations. An ANCOVA standardized effect size of 0.3 is equivalent to a Cohen's d of 0.60). To be conservative, a R-squared of 0 between the log_{10} viral RNA at 4-days and baseline log_{10} viral RNA was assumed. With a power of 90%, and a type I error rate of 20% (2-sided), it will be possible to detect the hypothesized 0.3 standardized effect size with 74 total patients – 37 patients per group with a 1:1 randomization. We will enroll a sample size of 142 to assure that a sufficient number of participants with baseline viral load >10⁵ copies/ml. The table below shows the power to detect an effect size of 0.3 given 10% loss to follow-up and various proportions enrolled with baseline viral load >10⁵ copies ml.

	Proportion of Enrolled Participants with >10⁵ copies/ml						
	0.40	0.50	0.60	0.70	0.80	0.90	1.00
Power to Detect Effect Size of 0.3	0.79	0.86	0.91	0.94	0.96	0.97	0.98

Based on available data regarding the distribution of viral load, it is conservatively estimated that \geq 50% of randomized participants will have a baseline viral load $>10^5$ copies/mL. The table above demonstrates that enrolling 142 will provide sufficient power even if the proportion with baseline viral load $>10^5$ copies/ml is as low as 40%. The prevalence of this subgroup will be monitored and adjustments to overall sample size may be made if necessary.

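### Section 5.1 uses 142 both as the number with baseline load at or above 10^5 and as the number randomised, which Section 12.2 contradicts; the synopsis also cites a cut-off adjustment that Section 12 does not contain

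*Combined protocol and SAP*

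**What the plan says.** **Size, Section 5.1.** The aim is at least 71 placebo participants at or above the assay limit on Day 4. To that end, 142 participants with baseline load of 10^5 copies/mL or above "will be enrolled to achieve the primary objective; thus, an expected 142 subjects will be randomized (71 to receive LAM-002A and 71 to receive placebo". Sections 5.1 and 5.3 then add that "this baseline viral load and number of participants randomized may be adjusted to allow for 71 placebo participants above the lower limit of detection".

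**Who can be enrolled.** Sections 6.1 and 6.2 contain no viral load criterion. Section 5.3 has the baseline swab taken before randomisation; "however, results on viral load will not be available prior to initiation of treatment".

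**Size, Section 12.2.** With 90% power and a two-sided type I error of 20%, "it will be possible to detect the hypothesized 0.3 standardized effect size with 74 total patients", that is, 37 per group. The 142 is total enrolment at any viral load. At least 50% are expected above 10^5, and the power table allows for 10% loss. The section concludes: "The table above demonstrates that enrolling 142 will provide sufficient power even if the proportion with baseline viral load" is as low as 40%. It adds: "The prevalence of this subgroup will be monitored and adjustments to overall sample size may be made if necessary".

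**The cut-off.** The synopsis says: "As existing data on viral load is preliminary, this baseline may be adjusted as detailed in the statistics section". Sections 12.1, 12.3.2 and 12.4.3 all define the primary population as above 10^5. Section 12.5 has the DSMB review the share above 10^5 at 50% enrolment and allows it to recommend a larger sample.

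**The concern.** Two sections give the same number, 142, different meanings. In Section 5.1 it is the size of the high-viral-load subgroup, and the randomised total follows from it. In Section 12.2 it is the randomised total, and the subgroup is a fraction of it. Both can be true only if every randomised participant is above the cut-off.

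The plan also lets the number randomised change during the trial. Section 5.1/5.3 ties that change to one target (71 detectable placebo participants). Section 12.2 works from another (74 evaluable in the subgroup, both arms together). A reader of 5.1 would expect a primary analysis about twice as large as the one Section 12.2 plans at its own 50% prevalence.

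The cut-off matters separately because it defines the primary analysis population. The synopsis, 5.1 and 5.3 allow it to move, and the place where the reader is told to find the details says nothing about moving it.

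**Working it through.** **Inputs.** From Section 12.2: two-sided alpha 0.20; power 0.90; ANCOVA effect size 0.3, equal to d = 0.60; R-squared 0 with baseline; 1:1 allocation; 142 enrolled; 10% loss; share above 10^5 at least 50%, tabulated from 40% to 100%. From Section 5.1: 142 at or above 10^5; 142 randomised; at least 71 placebo participants detectable at Day 4. The documents do not give the share of placebo participants still detectable at Day 4.

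**Step 1: reproduce Section 12.2.** Per arm, n = 2(1.2816 + 1.2816)^2 / 0.60^2 = 36.5, so 37, or 74 in total. Noncentral-t power (N − 3 degrees of freedom, noncentrality 0.60·√(N/4)) is 0.9005 at N = 74. The plan's figure reproduces.

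**Step 2: what 142 randomised delivers.** Number above 10^5 = 142 × share. Evaluable = that × 0.9. Evaluable placebo = half of the evaluable number.

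| Share above 10^5 | Above 10^5, both arms | Evaluable | Evaluable placebo | Power, recomputed | Power, Section 12.2 |
|---|---|---|---|---|---|
| 0.40 | 56.8 | 51.1 | 25.56 | 0.801 | 0.79 |
| 0.50 | 71.0 | 63.9 | 31.95 | 0.865 | 0.86 |
| 0.70 | 99.4 | 89.5 | 44.73 | 0.939 | 0.94 |
| 1.00 | 142.0 | 127.8 | 63.90 | 0.982 | 0.98 |

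The power table agrees to within about one percentage point. At no share does the evaluable placebo count in the subgroup reach 71. Reaching 74 evaluable from 142 randomised needs a share of 74/(142 × 0.9) = 0.579.

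**Step 3: what Section 5.1 would need.** The placebo arm is 71 and the target is at least 71 detectable, so there is no room for loss, for a baseline below the cut-off or for clearance by Day 4. Even with everyone above 10^5 and no loss, the chance that all 71 are detectable is q^71. For an assumed independent individual detectability q of 99%, 95% or 90%, that is 0.49, 0.026 or 0.0006.

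To have 142 participants above 10^5, the randomised total is 142/share: 355 at 40%, 284 at 50%, 203 at 70%, 142 at 100%. Adding 10% loss at 50% gives 142/(0.9 × 0.5) = 315.6, so 316. The 316 also assumes that all 71 detectable placebo participants must lie in the subgroup, that all evaluable ones there are detectable, and that the cut-off stays fixed. The adjustment sentence in 5.1 and 5.3 does not state the subgroup restriction. Without it, and with everyone detectable, 10% loss alone gives 142/0.9 = 157.8, so 158, whatever the share.

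**Step 4: the cut-off, side by side.** The synopsis, 5.1 and 5.3 permit a change; 5.1 and 5.3 name a goal for it. Sections 12.1, 12.3.2 and 12.4.3 use above 10^5 without qualification. Sections 12.2 and 12.5 change only the sample size. The reference in 12.5 to further details in the SAP follows the sentences on a sample size increase and conditional power, not on the cut-off.

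**The case against.** The strongest reply is that nothing in the planned primary test is affected. The randomised total is 142 in Sections 5.1, 5.3 and 12.2, the power calculation is right, and Section 12 fixes the primary population. The sample size may be raised, and the subgroup count that 12.5 wants to secure reads most naturally with 12.2. All of that stands. It leaves 12.5 silent on which count it means, and it leaves 5.1/5.3 tying changes in the randomised number to a different target.

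A further reply is that Section 5.2 covers adaptation: "The DSMB will be responsible for reviewing the interim safety and efficacy analyses and recommending study continuation, termination, or adaptation". That is a general role; it gives no rule for moving the cut-off. The detailed SAP might hold one, but the synopsis points to the statistics section and the text there has none.

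Stronger readings are tempting and not supported:

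- **The DSMB would face opposite instructions at 50% enrolment.** Section 12.5 gives it the share above 10^5 to review, not a count of detectable placebo participants at Day 4.
- **The trial needs at least 316, or 174 more than planned.** Those totals rest on the conditions in Step 3. They are not minima.
- **The trial is underpowered, or type I error is inflated.** Section 12.2 states its power openly at each prevalence, and no data-driven change of cut-off is laid out from which inflation could be judged.

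**Conclusion.** The point holds as a consistency fault in the 5.1/5.3 text and in the synopsis cross-reference, not in the power calculation. On Section 12.2's own inputs at 50% prevalence, 142 randomised yields about 71 participants above 10^5 in both arms together, where Section 5.1 states 142. It yields about 32 evaluable placebo participants above 10^5, where Section 5.1 aims for at least 71 detectable. Power is 0.86. Having 142 above 10^5 would take about 284 randomised at that prevalence, or about 316 under the added conditions in Step 3.

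These counts rest on 12.2's prevalence and loss assumptions, which 5.1 does not state. The mismatch itself needs only two facts: enrolment cannot be restricted by baseline load, and 12.2 does not expect everyone to exceed the cut-off.

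The permission to move the cut-off has a stated goal but no procedure in Section 12. The differences between at or above and above 10^5, and between 2 × 10^3 and 2228 copies/mL, are editorial.

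**What to change.** Reconcile 5.1 and 5.3 with 12.2 and say which basis governs.

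**If 12.2 governs**, as its reproducible calculation suggests:

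- Restate 5.1 and 5.3 as 142 randomised in total, with about 71 expected above 10^5 and about 64 evaluable at 50% prevalence (power 0.86), and 74 evaluable needed for 0.90.
- State in 12.5 that the subgroup number to be secured is the 12.2 count.
- Delete the permission to move the cut-off from the synopsis, 5.1 and 5.3.

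This adds no patients and leaves power unchanged. If the sponsor then chooses to secure 74 evaluable at 50% prevalence, the total becomes 74/(0.9 × 0.5) = 164.4, so 165, which is 23 more. The cost is a design choice as well as wording: the sponsor gives up the 71-detectable-placebo target, for which 12.2 has no equivalent, and the option to move the cut-off.

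**If the sponsor keeps either one**, restate the 142 and the 12.2 figures to match. For the 71 target, state whether the 71 must lie in the subgroup and what detectable share is assumed. For a movable cut-off, put the rule, data source, decision-maker and blinding in Section 12. The added enrolment depends on those choices; 142 participants above 10^5 at 50% prevalence would mean 284 − 142 = 142 more, before loss.

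No new Day 4 detectability endpoint is needed: Section 4.3.2 already compares the arms on the proportion below the LLOQ in nasopharyngeal samples. At most, report it in the primary population as well. Align the two editorial differences in the same revision.
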